## 5. STATISTICAL CONSIDERATIONS

### Design

This is a single-arm, open label, phase II trial to determine the progression free survival (PFS) of patients with multiple myeloma treated with the combination of MLN 9708 with Lenalidomide as maintenance therapy post autologous stem cell transplant.

### Analysis plan, Sample Size and Power

The primary endpoint is PFS, defined as the time from autologous stem cell transplantation (ASCT) to the time of clinical progression, death, whichever occurs first or the time of last contact. It is hypothesized that the combination will prolong PFS compared to the current standard regimen. A total of 48 patients (dosed at 3 mg of Ixazomib) will be enrolled at an accrual rate of 2 patients per month over 24 months. Additional 48 months of follow-up is planned after the last patient is recruited into the trial. Assuming that PFS time follows an exponential distribution, and patients treated with the current standard regimens had a median PFS of 40 months, we will monitor the PFS using the method of Thall et al. (Thall, 2005). Let  $T_s$  and  $T_e$  represent the time to progression for the standard regimens and the proposed treatment regimen, respectively. We assume  $T_s|M_s$  and  $T_e|M_e$  follow an exponential distribution with respective median  $M_s$  and  $M_e$ . Furthermore, we assume that the prior for  $M_s$  follows an inverse gamma distribution  $IG(100, 3960)$  to reflect our knowledge of PFS for the patients treated with the standard regimens. This has a mean of 40 months, and a variance of 16.3. The prior for  $M_e$  is assumed to be  $IG(3, 80)$ , which has the same mean of 40 months and a larger variance of 1600 to reflect the uncertainty about the median PFS of the proposed treatment regimen.

The PFS will be monitored every six months, and the study will be terminated early if there is little evidence based on the available data that the median PFS of the patients treated with the proposed treatment regimen is 12 months or more than that of the patients treated with the standard regimens. The formal stopping rule is

$$\Pr(M_e > M_s + 12 \mid \text{data}) < 0.035$$

Specifically, the trial will be stopped early if there is less than 3.5% chance that the median PFS for the patients treated with the proposed treatment regimen is 12 months or more than the median PFS for the patients treated with the standard regimens. The probability cutoff 0.035 was chosen to obtain an early stopping probability around 10% (0.091) if the true median PFS for the proposed treatment regimen results in a 12 months improvement over the historical median PFS of 40 months.

The operating characteristics of this decision rule are summarized in Table 1 using the onearmTTE software developed at the Department of Biostatistics at M.D. Anderson.

Table 1. Operating characteristics for the design (based on 2000 simulations)

True median Progression Free Survival (month)	Pr(stop early)	Average Number of Patients Treated (25th, 75th percentiles)
30	0.92	39.6 ( 32, 48 )

36	0.64	42.9 ( 42, 48 )
40	0.41	44.4 ( 48, 48 )
48	0.16	46.0 ( 48, 48 )
52	0.091	46.5 ( 48, 48 )
60	0.053	46.9 ( 48, 48 )

This monitoring will be carried out via the Clinical Trial Conduct (CTC) website (<https://biostatistics.mdanderson.org/ClinicalTrialConduct>) which is housed on a secure server at MDACC and maintained by the MDACC Department of Biostatistics. Access to the website will be gained through usernames and passwords provided by the MDACC Department of Biostatistics. Training on the use of the CTC will be provided by the biostatistical collaborator of the study, with emphasis on the importance of timely updating of follow-up times and recording of events. The monitoring rules for the PFS will be applied every six months with the probability criterion recomputed based on the most recent data available at that time. If the stopping rule is met, the study statistician, research nurse, and principal investigator will each receive an email notification that the stopping boundary has been met.

Because of the limited number of patients who have received the combination treatment, we will monitor the toxicity of the combination while we monitor the efficacy of it. Due to the lack of detailed information about the association between toxicity and efficacy, independency between the efficacy endpoints and toxicity endpoints is assumed, and the toxicity events are monitored continuously (Thall et al., 1996). The toxicity endpoint is defined as treatment-related unmanageable toxicities, including grade 3 non-hematologic effects, or grade 4 hematologic effects, that require delay or termination of the treatment during cycle 1. A toxicity rate of 30% or higher will not be considered acceptable. The prior probability of toxicity is assumed to follow a Beta (0.3, 0.7) distribution with one patient worth of information. The toxicity will be monitored by a cohort size of 4. At any time after at least 4 patients have completed toxicity evaluations, the trial will be stopped if the following statement is true

$$\Pr[\text{toxicity rate} > 30\% \mid \text{data}] > 0.95,$$

which means that the trial will be stopped for toxicity if the posterior probability of the toxicity rate being greater than 30% is greater 95%. The early stopping boundaries for toxicity, shown in the format of

(The number of patients with toxicities) / (The number of patients treated),  
are  $\geq 3/4$ ,  $5/8$ ,  $7/12$ ,  $9/16$ ,  $10/20$ ,  $12/24$ ,  $13/28$ ,  $15/32$ ,  $16/36$ ,  $18/40$ ,  $19/44$ , and  $21/48$ .

Table 2. Operating characteristics for the stopping rules  
For excessive toxicity monitoring

True DLT Rate	Probability Stop Early	Mean sample size
0.20	0.035	46.5
0.30	0.18	41.8
0.40	0.56	30.7
0.45	0.77	23.8
0.50	0.91	17.8

Early termination of the trial can be caused by either lack of efficacy or excessive toxicity. If the efficacy and toxicity are considered jointly, the early stopping probabilities as shown in Table 3 will be higher than the probabilities shown in Tables 1 to 2.

Table 3: Operating characteristics considering efficacy and toxicity jointly

True median	True toxicity rate	Probability Stop Early
36	0.2	0.65
36	0.3	0.70
36	0.5	0.97
52	0.2	0.12
52	0.3	0.25
52	0.5	0.92
60	0.2	0.086
60	0.3	0.22
60	0.5	0.91

Patients' demographic and clinical characteristics at baseline will be summarized using descriptive statistics such as frequency distribution, mean ( $\pm$  s.d.) and median (range) accompanied by graphical analysis. Student t-test/Wilcoxon test and ANOVA/Kruskal-Wallis test will be used to compare continuous variables between different patient groups. The chi-square test or the Fisher's exact test will be applied to assess the association between two categorical variables (Woolson, 2002).

The response rates and incidence of new primary malignancy will be estimated along with 95% confidence intervals. Time-to-event outcomes, including PFS and overall survival (OS), will be estimated using the Kaplan-Meier method (Kaplan, 1958). log-rank test will be performed to test the difference in time-to-event distributions between patient groups (Mantel, 1966). Cox proportional hazards model will be used to include multiple covariates in the time-to-event analysis (Cox, 1972).

Toxicity data will be summarized by frequency tables. For the toxicity endpoint, per-treated analysis will be used to include any patient who received the treatment regardless of the eligibility nor the duration or dose of the treatment received.

The MDASI –myeloma symptom evaluation will be analyzed with descriptive analysis.

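### PFS is dated from transplant but patients enter 60 to 180 days later: the endpoint text and Table 1's patients-treated column cannot both describe the futility rule

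*Combined protocol and SAP*

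**What the plan says.** Section 5 (Analysis plan, Sample Size and Power) gives the endpoint: "The primary endpoint is PFS, defined as the time from autologous stem cell transplantation (ASCT) to the time of clinical progression". It says that PFS is what will be monitored. It then introduces the model variables, which "represent the time to progression for the standard regimens and the proposed treatment regimen, respectively", without giving them a starting point.

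Sections 3.1 and 3.2.1 let maintenance start no earlier than 60 and no later than 180 days after transplant.

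On looks, Section 5 says "The monitoring rules for the PFS will be applied every six months", and on duration, "Additional 48 months of follow-up is planned after the last patient is recruited into the trial". It does not say whether looks continue through that follow-up. For the final analysis, "Time-to-event outcomes, including PFS and overall survival (OS), will be estimated using the Kaplan-Meier method". Left truncation, delayed entry and landmarking are not mentioned.

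The 40-month benchmark also has no stated clock start. Sections 1.1 and 1.4 cite 40+ and 42 months for lenalidomide maintenance. Section 1.4 describes one of these results as post-transplant PFS, which does not settle where time began.

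**The concern.** A patient who dies between transplant and first dose cannot enter the trial. Exclusion of patients who progress in that gap is not written into Section 3.2; it is inferred from the maintenance setting and from removal for progression in Section 3.9. Each enrolled patient therefore brings waiting time that carries exposure but no event. The futility rule depends only on the event count and total exposure, so this time makes the new regimen look better early on, when little real follow-up exists.

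Only a stop during accrual spares patients from enrolment. If the rule runs from transplant, Table 1 promises more of that protection than the rule gives. If it runs from entry, the endpoint text describes something other than what is monitored.

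**Working it through.** **Inputs (Section 5 unless noted).** 48 patients at 2 per month; priors IG(100, 3960) for the standard median M_s and IG(3, 80) for the new median M_e; stop if Pr(M_e > M_s + 12 | data) < 0.035; looks every 6 months; 48 months of follow-up after the last patient. Wait from Sections 3.1 and 3.2.1: 60/30.44 = 1.97 to 180/30.44 = 5.91 months.

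**Assumed.** Poisson accrual. Waits all 60 days, all 180 days, or uniform between (mean 3.94 months). Two look schedules: (A) looks during accrual plus one final look; (B) looks throughout plus the final one.

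**Priors.** 3960/99 = 40 and 40²/98 = 16.3; 80/2 = 40 and 40²/1 = 1600. Both agree with the text.

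**Rule.** With d events and total exposure T, the posterior of M_e is IG(3 + d, 80 + ln2 × T). The trial stops when T is below a boundary: 108.6 patient-months at 4 events, 157.5 at 5, 207.9 at 6, 259.5 at 7.

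**What the wait does at month 12.** About 24 patients have been enrolled for 6 months on average, which gives 144 patient-months, or about 134 after time lost to events at a true median of 40.
- No wait: 134 lies between 108.6 and 157.5, so 5 events stop the trial.
- Uniform wait: 134 + 24 × 3.94 = 229, so 7 events are needed.
- All 60 days: 134 + 47 = 181, so 6. All 180 days: 134 + 142 = 276, so 8.

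**Reproducing Table 1 with the clock at entry, schedule A** (20,000 trials per row; 12,000 per row with waits), at medians 30/36/40/48/52/60:
- Pr(stop) 0.92/0.64/0.42/0.16/0.107/0.05; stated 0.92/0.64/0.41/0.16/0.091/0.053.
- Mean treated 39.9/43.0/44.3/45.9/46.4/47.0; stated 39.6/42.9/44.4/46.0/46.5/46.9.

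**Adding the wait.** *Shared clock* means that benchmark and true median both run from transplant with the same wait, so the post-entry median is m minus the mean wait. *First-dose clock* means that both run from first dose, so the post-entry median is m. The first-dose figures also cover exponential PFS from transplant, conditional on being event-free at entry.

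| Case | Mean treated at 30 (25th percentile) | Mean treated at 36 |
|---|---|---|
| Table 1 | 39.6 (32) | 42.9 |
| No wait | 39.9 (32) | 43.0 |
| Shared, 60 days | 42.5 (40) | 45.0 |
| Shared, uniform | 44.4 (47) | 46.4 |
| First-dose, 60 days | 43.5 (44) | 45.6 |
| First-dose, uniform | 45.9 (48) | 47.1 |
| First-dose, 180 days | 47.1 (48) | 47.7 |

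This column depends only on looks during accrual, so schedules A and B give the same values. Chance does not explain the gap: in forty runs of 2,000 trials at 30, the mean was 39.4 to 40.3 with no wait and 42.1 to 42.9 with 60-day waits. The excess over Table 1 at 30 runs from 42.5 − 39.6 = 2.9 to 47.1 − 39.6 = 7.5 patients.

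**Stopping during accrual** (either schedule), no wait, then the range from all 60 to all 180 days:
- At 30: 0.48; shared 0.35 to 0.19; first-dose 0.29 to 0.06.
- At 40: 0.21; shared 0.12 to 0.03; first-dose 0.09 to 0.01.

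**Overall stopping, uniform wait** (A, then B):
- At 30 (stated 0.92): shared 0.94, 0.96.
- At 40 (stated 0.41): shared 0.36, 0.43; first-dose 0.18 under A.
- At 52 (stated 0.091): shared 0.03, 0.05; first-dose 0.013, 0.02.

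**Table 3** equals 1 − (1 − Table 1)(1 − Table 2) in every row. For example, median 52 and toxicity 0.2 give 1 − 0.909 × 0.965 = 0.12. It inherits any change in Table 1.

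**The case against.** **Monitoring may run from entry.** The model variables have no stated origin, and the documents do not say how the monitoring website counts time. If the count starts at entry, no stopping is lost. This stands: a reader might infer a demonstrated loss of stopping, but what the documents establish is a mismatch between text and table.

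**Overall stopping may hardly change.** A reader might infer that the futility rule is broadly weakened. On a shared clock it is not: stopping at 30 does not fall, and wrongly stopping a regimen that meets the 52-month target becomes rarer. The Pr(stop) column does not identify the clock either. A shared clock with 60-day waits under schedule B gives 0.95/0.69/0.47/0.16/0.09/0.03, within 0.06 of Table 1 in every row. The case therefore rests on the patients-treated column and on stopping during accrual.

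**The fit to an entry clock is conditional.** Monthly looks with every wait at 60 days and a shared clock give 38.7/42.6/44.3/46.0/46.5/47.1, near the column, but this contradicts the stated six-monthly looks. With evenly spaced accrual the mean at 30 is 41.6 without a wait and 43.3 with 60 days. Neither matches 39.6, and the wait moves further away.

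**The final analysis.** A reader might infer a biased comparison of the Kaplan-Meier median with 40 months. Section 5 plans no such test, and the benchmark's origin is unknown. PFS from transplant among patients who reach maintenance is a legitimate descriptive figure if labelled as such.

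**Conclusion.** The concern holds in a limited form. Given six-monthly looks and Poisson accrual, the endpoint definition and Table 1 cannot both describe the monitoring rule. If monitoring runs from entry, Table 1 stands and the text must change. If it runs from transplant, stopping during accrual at a true median of 30 falls from about 0.48 to 0.19–0.35 (shared clock) or 0.06–0.29 (first-dose clock), with about 3 to 7.5 more patients treated than Table 1 shows. That direction holds on both look schedules and both benchmark clocks. The size of the loss depends on the unknown distribution of waits. The effect on overall stopping cannot be settled without the benchmark's time origin and the look schedule after accrual. This should be fixed, at moderate priority.

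**What to change.** 1. State the time origin of the 40-month benchmark, the clock used in monitoring, and whether looks continue after accrual.
2. Put the monitoring likelihood and both priors on one clock, counting exposure from first maintenance dose or left-truncating there. If the benchmark runs from transplant, re-base both priors first. With a shared uniform wait, 40 − 3.94 = 36.06 gives about IG(100, 3570) and IG(3, 72). Moving the clock without re-basing in that case raises Pr(stop) at 52 to about 0.16 (schedule A) or 0.22 (schedule B).
3. Re-run Tables 1 and 3. Re-tune 0.035 only if the re-run no longer gives about 0.09 at 52 months. With a first-dose benchmark and schedule A, delayed entry alone returns the entry-clock figures (0.103 at 52), so no re-tuning is needed. Under schedule B the entry clock gives about 0.15, so step 1 matters here too. The re-based shared case gives 0.11 (A) or 0.15 (B).
4. Keep PFS from transplant as a descriptive Kaplan-Meier estimate, labelled as conditional on reaching maintenance.

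The cost is SAP wording, one re-simulation and finding the benchmark's origin. Transplant and first-dose dates are already needed for eligibility. If the clock moves, the monitored median is about 2 to 6 months shorter than the one counted from transplant.

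### The plan hypothesises longer PFS, but its final analysis never tests this against the 40-month benchmark or the 12-month target, and finishing unstopped cannot stand in for that test

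*Combined protocol and SAP*

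**What the plan says.** All of this is in Section 5 of the combined protocol and SAP.

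- **Aim.** Under Design: "This is a single-arm, open label, phase II trial to determine the progression free survival (PFS) of patients with multiple myeloma".
- **Hypothesis.** Under Analysis plan, Sample Size and Power: "It is hypothesized that the combination will prolong PFS compared to the current standard regimen". The benchmark is that "patients treated with the current standard regimens had a median PFS of 40 months", under an exponential model.
- **Model.** Ms has prior IG(100, 3960): "This has a mean of 40 months, and a variance of 16.3". Me has prior IG(3, 80), "which has the same mean of 40 months and a larger variance of 1600".
- **Size.** The 48 patients "will be enrolled at an accrual rate of 2 patients per month over 24 months". Follow-up then runs for a further 48 months from the last entry.
- **Decision rule for PFS.** Stop if Pr(Me > Ms + 12 | data) < 0.035, checked every six months. The cutoff was chosen so that a regimen with a true median of 52 months is stopped about 10% of the time (0.091). A separate rule stops for toxicity.
- **Final analysis.** "Time-to-event outcomes, including PFS and overall survival (OS), will be estimated using the Kaplan-Meier method". A log-rank test between unspecified patient groups and a Cox model follow. Response rates and new malignancies are promised 95% confidence intervals; no interval is named for PFS.

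No posterior threshold, confidence limit, alpha or power is given for concluding that PFS was prolonged, although the subsection title mentions power.

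**The concern.** The plan poses a comparative question and builds a model that could address it, then uses the model in one direction only: to give up early. At the end of follow-up nothing in Section 5 sets the PFS result against 40 months or against 40 + 12 = 52 months. The log-rank test cannot fill the gap, because the trial has one arm and the standard regimen is represented only by a prior.

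This leaves the reading of the result to be chosen after the data are seen. The only formal PFS statement available would be that the futility boundary was not crossed, and someone could present that as support for the hypothesis. The futility rule was tuned to protect a regimen that reaches 52 months. It was not tuned to limit a favourable reading of one that stays at 40.

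**Working it through.** **1. Priors.** For IG(a, b) the mean is b/(a − 1) and the variance is mean²/(a − 2).
- Ms: 3960/99 = 40; 40²/98 = 16.3.
- Me: 80/2 = 40; 40²/1 = 1600.

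Both agree with Section 5.

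**2. Posterior.** With d events and total time at risk T under an exponential model, Me | data ~ IG(3 + d, 80 + ln 2 × T). Ms keeps its prior, because there is no control arm. Everything needed for a final comparison is therefore already in the plan.

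**3. Reproducing Table 1.** Simulation used Poisson accrual at 2 per month and 48 patients, with six-monthly looks during accrual and one look at the end of the 48-month follow-up (20,000 trials per row).

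| True median (months) | Table 1 Pr(stop) | Simulated Pr(stop) | Unstopped, 1 − Table 1 |
|---|---|---|---|
| 30 | 0.92 | 0.917 | 0.08 |
| 36 | 0.64 | 0.635 | 0.36 |
| 40 | 0.41 | 0.425 | 0.59 |
| 48 | 0.16 | 0.167 | 0.84 |
| 52 | 0.091 | 0.107 | 0.909 |
| 60 | 0.053 | 0.051 | 0.947 |

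All rows agree within 2 percentage points. The Monte Carlo standard error of the plan's 0.41 is √(0.41 × 0.59/2000) = 0.011.

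**4. Look schedule.** The text says looks occur every six months and does not say that they end with accrual. If they continue through follow-up, Pr(stop) at 40 months is about 0.51 to 0.53, so about 47% to 49% finish unstopped. Table 1 and the text thus appear to describe different schedules.

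**5. Adding the toxicity stop.** Under the plan's independence assumption, the joint stopping probability is 1 − (1 − p)(1 − q). This reproduces Table 3; for example, 1 − 0.36 × 0.965 = 0.65 at 36 months and 20% toxicity. At a true 40 months the unstopped share is 0.59 × 0.965 = 0.57 with 20% toxicity and 0.59 × 0.82 = 0.48 with 30%.

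**6. What a final criterion would do.** The cutoffs here are illustrations; the documents give none. Success means not stopped and the posterior condition met at the end of follow-up. The clock starts at entry.

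| Criterion | 40 | 48 | 52 | 60 |
|---|---|---|---|---|
| Pr(Me > Ms) > 0.90 | 5% | 26% | 41% | 69% |
| Pr(Me > Ms) > 0.85 | 9% | 35% | 52% | 78% |

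The 0.90 figures are nearly the same under either look schedule; all figures move by a point or two between runs. About 26 events are expected in unstopped trials at a true 52 months. With 26 to 30 events, the 0.90 rule needs an observed exponential median of about 53 to 54 months.

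**7. Time origin.** Section 5 counts PFS from ASCT, but Sections 3.1 and 3.2.1 have maintenance start 60 to 180 days later. Time between transplant and entry is necessarily event-free for an enrolled patient. Assume entry uniform at 2 to 6 months after ASCT, mean 4 months. Counting it adds 48 × 4 = 192 patient-months to T with no events. With about 29 events, that lifts the estimated median by roughly ln 2 × 192/29 = 4.6 months. In simulation with the hazard unchanged and no correction, the 0.90 rule succeeds in about 14% of trials at 40 months and 64% at 52, and the 0.85 rule in about 22% at 40.

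**The case against.** The tempting stronger reading is that the plan has a 59% false-positive rate, with survival of the futility rule as its success criterion. The documents do not support that. The 0.035 rule is presented only as an early-stopping rule, and nowhere is an unstopped trial called a success. The 59% is the complement of a futility probability. It also belongs to the schedule behind Table 1; the text as written gives about 48%.

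Nor do the documents show that the trial cannot answer its question. The Design paragraph sets out to determine PFS, and for a single-arm phase II trial Kaplan-Meier estimation is a legitimate answer to that. The benchmark is in the plan, and Pr(Me > Ms + 12 | data) is recomputed at each look. The futility rule is not empty either: it stops 92% of trials at a true 30 months and 64% at 36, and its cost at 52 months is disclosed.

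Finally, a 0.90 cutoff is a preference. It has no source in the documents, tests any gain rather than the 12-month target, and would miss 1 − 0.41 = 59% of trials that truly reach 52 months.

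All of this stands, and it narrows the point. It does not remove it. If the aim is estimation, the comparative hypothesis has no analysis attached. If the aim is comparison, the final comparison is missing.

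**Conclusion.** The concern holds in a limited form. Section 5 states a comparative hypothesis and defines the model to address it, but the final analysis neither uses that model nor refers to 40 or 52 months. Not being stopped is not evidence of benefit: with no gain it happens in 59% of trials by Table 1, or in about 47% to 49% with six-monthly looks throughout follow-up.

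These figures assume exponential PFS, accrual at 2 per month, the stated priors, a clock that starts at entry and no toxicity stop. The gap itself depends on none of these; it is visible from the text. The success rates of any final cutoff do depend on them, and especially on the time origin: 5% becomes about 14% at 40 months if time since ASCT is counted uncorrected, given the assumed entry window. This should be settled before the final analysis; it does not invalidate the design.

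**What to change.** Add one paragraph to Section 5:

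- At the end of the planned 48-month follow-up, report Pr(Me > Ms | data), Pr(Me > Ms + 12 | data) and the posterior median of Me with a 95% credible interval, using the priors already stated. Place them beside the Kaplan-Meier median PFS with its 95% confidence interval.
- State that completing the trial unstopped will not by itself be read as benefit.
- Keep ASCT as the PFS origin if wished, but count time at risk from study entry (delayed entry), in the posterior and in the Kaplan-Meier risk sets.
- State one look schedule and make Table 1 agree with it.

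If a cutoff for calling the regimen promising is wanted as well, prespecify it and add its success probability to every Table 1 scenario under that one schedule. The 0.90 and 0.85 rules above show the kind of trade-off to expect.

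The alternative is to state that the PFS aim is estimation, name the interval to be reported, and reword the hypothesis sentence.

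The cost is a paragraph and a little extra analysis, plus a rerun of the simulation to align Table 1 with one schedule. If a cutoff is set, the plan must also disclose modest power at the 12-month target, for example about 41% with the 0.90 rule.

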#### **4.3 Long Term Follow-Up Phase**

Following end of therapy on this trial, all subjects will be followed until death, withdrawal of consent for study participation, or removal from study. Subjects will return to the site or be contacted by telephone every 6 months (+/- 4 weeks) for follow up assessments of the following:

- Second primary malignancies
- Next-line of therapy
- Progressive disease on next line of therapy
- Overall survival

Following disease progression on the next-line of therapy, subjects will only be followed for overall survival and development of 2nd primary malignancies.

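### The six-monthly PFS futility rule has no last look and no separate action once all 48 patients are enrolled, and Table 1 appears to have been computed on a different look schedule

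*Combined protocol and SAP*

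**What the plan says.** The design is in Section 5, Analysis plan, Sample Size and Power. Patients "will be enrolled at an accrual rate of 2 patients per month over 24 months", to a total of 48, so enrolment closes at about month 24. "Additional 48 months of follow-up is planned after the last patient is recruited into the trial", which takes the study to about month 72.

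PFS is monitored every six months, and "the study will be terminated early if there is little evidence based on the available data" that median PFS on the combination exceeds the standard by 12 months or more. The paragraph after Table 1 repeats the six-monthly schedule. Neither place gives a last look or limits the rule to the enrolment period. Neither says what a crossing does to follow-up when nobody is left to enrol. The cutoff of 0.035 was chosen so that a regimen with a true median of 52 months stops early about 10% of the time (0.091).

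Table 1 gives Pr(stop early) beside a column headed "Average Number of Patients Treated (25th, 75th percentiles". It does not state the look schedule simulated and does not split stops into those before and after full enrolment. Section 4.3 says that after therapy ends "all subjects will be followed until death, withdrawal of consent for study participation, or removal from study".

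**The concern.** A futility rule does two jobs while a trial is enrolling: it limits how many patients start an inactive regimen, and it ends the study. After the 48th patient only the second job remains. Section 5 leaves the same rule running through some four years of follow-up with termination as its only stated consequence.

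PFS is the primary endpoint, and second primary malignancy is a listed secondary objective (Sections 2.1 and 2.2). Both depend on long follow-up. If a late crossing did end the study, both would be frozen at a look selected because the data were unfavourable at that moment.

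There is also a calibration question. The value 0.091 is the stated justification for the cutoff, and it belongs to whatever look schedule was simulated. If that schedule is not the one in the text, the trial as written has a different chance of stopping a regimen that meets its target.

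**Working it through.** **Inputs (Section 5).** 48 patients at 2 per month; exponential PFS; Ms ~ IG(100, 3960); Me ~ IG(3, 80); stop if Pr(Me > Ms + 12 | data) < 0.035; looks every six months; 48 months of follow-up after the last enrolment.

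**Priors.** Ms: mean 3960/99 = 40, variance 40²/98 = 16.3. Me: mean 80/2 = 40, variance 80²/(2²·1) = 1600. Both agree with the text.

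**From Table 1 alone.**
- At a true median of 40 months the 25th percentile of patients treated is already 48, so at most about 25% of trials stopped short of 48. Since 41% stopped, at least about 0.41 − 0.25 = 0.16 stopped with everyone enrolled.
- At 30 months the 75th percentile is 48, so at least about 25% of trials reached 48. Only 1 − 0.92 = 0.08 did not stop. At least about 0.25 − 0.08 = 0.17 therefore stopped with everyone enrolled.

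**Simulation.** With d events and total follow-up T, the posterior of Me is IG(3 + d, 80 + T·ln 2). Ms is not updated. The rule becomes a boundary on T for each d: for example, stop at 12 events if T is below about 530 patient-months, and at 20 events if T is below about 990. The PFS clock starts at entry and there is no dropout. The table uses 60,000 trials per row with Poisson accrual at 2 per month.

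| True median (months) | Table 1 | Looks in accrual + one look 48 months after last entry: total (before / after full enrolment) | Six-monthly through month 72: total (before / after) |
|---|---|---|---|
| 30 | 0.92 | 0.913 (0.477 / 0.436) | 0.944 (0.478 / 0.466) |
| 36 | 0.64 | 0.640 (0.297 / 0.343) | 0.723 (0.295 / 0.428) |
| 40 | 0.41 | 0.428 (0.213 / 0.215) | 0.522 (0.211 / 0.311) |
| 48 | 0.16 | 0.167 (0.111 / 0.056) | 0.226 (0.110 / 0.116) |
| 52 | 0.091 | 0.107 (0.082 / 0.025) | 0.149 (0.082 / 0.067) |
| 60 | 0.053 | 0.051 (0.048 / 0.004) | 0.066 (0.045 / 0.020) |

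**Which schedule fits Table 1?** Mean N cannot tell, because looks after the 48th patient do not change N; both schedules give about the printed values. Pr(stop early) can tell. Table 1 rests on 2000 simulations, so the standard error at 52 months is √(0.091·0.909/2000) = 0.0064. The single-final-look figure is (0.107 − 0.091)/0.0064 = 2.5 standard errors away, and the six-monthly figure is (0.149 − 0.091)/0.0064 = 9. At 40 months the standard error is 0.011 and the distances are 1.6 and 10. The fit is close rather than exact. Stopping the looks at month 36 also fails: it gives about 0.77 at 30 months against 0.92.

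**Share of stops with all 48 enrolled, on the fitting schedule.** 48%, 54% and 50% at 30, 36 and 40 months; 34% at 48; 0.025/0.107 = 23% at 52; under a tenth at 60.

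**The literal reading (looks to month 66 or 72).** Terminations after full enrolment are about 0.30-0.34 at 40 months and 0.06-0.07 at 52. They come on average around months 37-43 with about 20-22 events. Mean follow-up at month 72 is about 60 months, so full follow-up would give about 48·(1 − 2^(−60/40)) = 31 events at 40 months and 48·(1 − 2^(−60/52)) = 26 at 52.

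**Sensitivity to accrual.** Stops before full enrolment are 0.18 (even spacing from month 0) to 0.21 (Poisson) at 40 months, and 0.07 to 0.08 at 52. Even spacing from month 0.5 gives about 0.14 and 0.05, with late stops of about 0.36 and 0.08 and a total of about 0.13 at 52 months.

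**Table 3.** At 52 months and toxicity 0.2, 1 − (1 − 0.091)(1 − 0.035) = 0.123, which is the printed 0.12. With 0.149 it becomes 1 − 0.851·0.965 = 0.18.

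**The case against.** **Follow-up may survive a crossing.** Section 4.3 follows every subject until death, withdrawal of consent or removal from study. Section 3.9 lists the removal reasons, and a futility crossing is not one of them. Section 5 describes a crossing operationally as an email to the statistician, research nurse and principal investigator. A reader might infer that the protocol orders follow-up to end; it does not say so. It is silent, and the word for the study is still terminated. This stands as a reason to call the point an ambiguity.

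**Table 1 does not show lost follow-up.** A reader might infer from the late stops in Table 1 that the tabulated rule cuts off the planned 48 months. On the schedule that fits the table, those stops fall when follow-up is already complete. The truncation risk comes from the text. The timing and event counts for late terminations describe the literal reading of the text, not what Table 1 measures.

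**The share is not large in every row.** It is near half only at 30-40 months, where stopping is the right decision. It is about a quarter at the 52-month target and under a tenth at 60. It would be wrong to say that most of the column is hollow.

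**A late stop is not necessarily empty.** Treatment has no fixed duration in Section 3.9, so a crossing could matter to patients still on therapy. The documents do not say how.

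**Confining the rule to enrolment is costly.** This is the only formal PFS decision rule in Section 5. Limiting it to accrual would cut Pr(stop) at a true median of 30 months from 0.92 to about 0.41-0.48. That objection is sound, and the change is not proposed here.

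**Conclusion.** The point holds as a gap between text and table, with a follow-up risk if the text is taken literally. Section 5 gives a six-monthly terminating rule with no end and no distinct action after the 48th enrolment. Applied that way, it stops about 0.14-0.15 of trials at the 52-month target (0.13 under one accrual variant) against the stated 0.091. It also terminates roughly three in ten trials at 40 months after everyone is enrolled, with about two-thirds of the events that full follow-up would give (20-22 of about 31).

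The only conclusion that needs no simulation is that at least about 16 of the 41 points at 40 months are stops with all 48 patients enrolled. The rest assumes exponential PFS counted from entry (Section 5 counts from transplant, and therapy starts 60-180 days later), no dropout and no reporting lag. The schedule behind Table 1 is inferred from the match and should be confirmed with whoever ran the software.

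**What to change.** In Section 5:

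1. State the PFS look schedule in full, including the last look.
2. State that a crossing after the 48th patient is enrolled is reported as a futility conclusion and does not end PFS, second-malignancy or survival follow-up, which continues as planned in Sections 4.3 and 5. The protocol should also say whether such a crossing has any consequence for patients on therapy; that is for the sponsor-investigator to settle.
3. Rerun Tables 1 and 3 on the stated schedule, state that schedule under the tables, and report the probability of stopping before and after full enrolment separately. The before-enrolment figures should be about 0.18-0.21 at 40 months and 0.07-0.08 at 52, lower under the late-start variant above.

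The cost is protocol wording and a simulation rerun, with no added patients, visits or procedures. The drawback is one of presentation and calibration. The part of the stopping probability that limits enrolment becomes visibly smaller than the printed 0.41 at 40 months. If six-monthly looks through follow-up are kept, the 0.091 rises to about 0.14-0.15 and the choice of 0.035 has to be justified again or revisited.
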